5.2 PACE OF ENROLLMENT

During the Phase I study, approximately two thirds of subjects enrolled qualified for vaccination. Taking into account the screen-failure rate and attrition rate (currently about 5% per year), we plan to enroll 125 subjects for screening, and to initiate vaccination in 80 subjects.

5.3 STUDY DURATION

The study duration will be up to 66 months. Each subject is expected to be in the study for approximately 16 months or longer if LEEP is performed.

6 STUDY VISITS

6.1 SCHEDULING STUDY VISITS

The Study Coordinator will schedule study visits (Screening, Vaccination, 6-Month, 12-Month, and Optional LEEP Visits) at the UAMS Obstetrics and Gynecology Clinics and the UAMS Winthrop P. Rockefeller Cancer Institute (WPRCI). The Screening, 6-Month, 12-Month, and Optional LEEP Visits are expected to take approximately 90 minutes. However, they may be longer on busy clinic days. Vaccination Visits are expected to take approximately 60 minutes.

6.2 STUDY VISIT WINDOWS

6.2.1 Between Visits of an Individual Subject

- The first vaccination visit (Visit 1) should be scheduled as soon as possible after all results from the screening visit are available, and subjects are deemed qualified to continue to the vaccination phase of the study, but no later than 60 days after the day punch biopsy was obtained (the screening day for most of the subjects).
- The subsequent vaccination visits (Visits 2-4) should be scheduled 3 weeks \pm 7 days apart.
- The 6-Month Visit should be scheduled 6 months \pm 2 weeks following Visit 4
- The 12-Month Visit should be scheduled 6 months \pm 2 weeks following 6-Month Visit.
- Optional LEEP visit (if subject chooses) should be scheduled as soon as possible after 12-Month Visit or after determining a subject needs to be withdrawn due to serious toxicity.

6.3 STUDY VISIT LOCATIONS

6.3.1 Screening Visit

UAMS Obstetrics and Gynecology Clinics

6.3.2 Vaccination Visits

WPRCI Infusion center 1

6.3.3 6-Month, 12-Month, Optional LEEP Visits

UAMS Obstetrics and Gynecology Clinics

6.3.4 Optional Follow-Up Visits (If necessary)

UAMS Obstetrics and Gynecology Clinics or UAMS WPRCI

6.4 SCREENING VISIT

6.4.1 Procedures for Screening Visit

- Review inclusion/exclusion criteria
- Obtain informed consent (if not previously obtained)
- Have the subject fill out “Subject Contact Information” during the visit
- Have the subject fill out “Screening Visit Questionnaire” during the visit
- Obtain demographic information
- Obtain subject’s history
 - Medical history: Be sure to ask for history of previous abnormal Pap smears and how they were treated
 - Drug allergies
 - Concomitant medications
- Perform a physical examination
 - Obtain vital signs
 - Blood pressure (<200/120 mm Hg acceptable)
 - Heart rate (50–120 beats per min acceptable)
 - Respiratory rate (<25 breaths per min acceptable)
 - Temperature (<100.4°F)
 - Weight (no restriction)
- For a subject with child-bearing potential
 - Discuss the risks involved in becoming pregnant while receiving vaccine
 - Ask which birth-control method she will be using while participating in the vaccine trial; FDA acceptable forms of preventing pregnancy include oral contraceptives, contraceptive patches/rings/implants/shots, double-barrier methods (e.g. condoms and spermicide), abstinence and/or vasectomies of a male partner with a documented second acceptable method of birth control
 - Ask if subjects need the study to provide birth control and discuss options. All of the options below are available to subjects free of charge while participating in the study.
 - Sprintec is an oral contraceptive and it is available throughout the study.
 - Low-Ogestrel is an oral contraceptive and it is available throughout the study for subjects who need to be taken off Sprintec for medical reasons.
 - Depo-Provera is a contraceptive given as a shot every 3 months and it is available throughout the study.
 - Liletta is an intrauterine device contraceptive and is available only during the first 3 months of participation. An exception would be allowed if an existing IUD were

removed during one of the study visits. In this situation, the IUD may be replaced with Liletta throughout the study.

- The study will cover the cost of the IUD, IUD placement within the first 3 months of study participation (with the exception of replacing an IUD removed during study visits), and IUD removal during your study participation, but not afterwards.
- Perform colposcopy
 - Obtain ThinPrep for HPV-DNA testing
 - Obtain punch biopsy and endocervical curettage if determined to be necessary by the physician (HSIL needs to be confirmed to be eligible)
 - Physician may acquire four-quadrant blind biopsy if no areas of lesions are visible upon colposcopy
 - Record the lesion(s), locations on the cervix, image cervix using the colposcope-mounted image capture system (if available), and indicate where biopsy was taken
 - Record in how many cervical quadrants the lesions are visible
 - If the subject has already been diagnosed with HSIL by biopsy, there is no need to repeat it. However, colposcopy could be repeated to document the location of the lesion(s), and to collect ThinPrep for HPV-DNA and bacterial testing.
 - Colposcopy may be performed in the OR if medically necessary. A COVID-19 test may be required per hospital policy prior to intervention in the OR.
- Draw blood tubes for complete blood count (CBC), and comprehensive metabolic panel (CMP) (to be performed in UAMS clinical laboratory)
 - Comprehensive metabolic panel (CMP) testing
 - Alanine transaminase (no restriction)
 - Aspartate transaminase (no restriction)
 - Albumin (no restriction)
 - Alkaline phosphatase (no restriction)
 - Total bilirubin (no restriction)
 - Total protein (no restriction)
 - Sodium (no restriction)
 - Potassium (no restriction)
 - Chloride (no restriction)
 - CO₂ (no restriction)
 - Blood urea nitrogen (no restriction)
 - Creatinine (no restriction)
 - Calcium (no restriction)
 - Glucose (no restriction)
 - Complete Blood Count (CBC) testing
 - White count ($>3 \times 10^9/L$ acceptable)
 - Hemoglobin ($>8 \text{ g/dL}$ acceptable)
 - Hematocrit (no restriction)
 - Platelet count ($>50 \times 10^9/L$ acceptable)

6.4.2 Follow-Up to the Screening Visit

The Study Coordinator and Principal Investigator or Co-Investigator will review all information and test results from the screening visit, and will determine whether the subject is eligible to receive vaccination. Eligibility for vaccination includes presence of HSIL or “cannot rule out HSIL” by colposcopy guided biopsy, no evidence of invasive squamous cell carcinoma, vital signs within certain limits, and certain blood tests within acceptable ranges.

- If eligible for vaccination, schedule vaccination visits at WPRCI Infusion center 1
- If not eligible for vaccination, inform subject via phone call, and schedule a follow-up visit if necessary. If a subject has a condition, which requires further medical care, including invasive squamous cell carcinoma, study physicians will refer her to receive appropriate medical care.

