Diagnosis and Main Inclusion Criteria	Recent Pap smear result consistent with HSIL or “cannot rule out HSIL” or recent untreated colposcopy guided biopsy-confirmed HSIL
Eligibility for Vaccination	Recent untreated colposcopy guided biopsy-confirmed HSIL
Study Product(s), Dose, Route, Regimen	Test Article: Vaccine consisting of four HPV 16 E6 peptides in combination with Candin® (PepCan) or Candin® alone Route of Administration: Intradermal injection Peptide Dose Level: 50 µg/peptide/injection based on the clinically optimal dose from the Phase I study Candin® Dose Level: 300 µl/injection for PepCan and Candin® groups Dosing Regimen: 4 injections; three weeks between each injection Injection site: Limbs
Statistical Methodology	Clinical response data (PepCan or Candin®) will be compared to a historical placebo control group from a similarly designed clinical trial using appropriate statistical tests; measures of safety will be evaluated using descriptive statistics.

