1.5.9 Rationale for Primary Outcome Measure: Efficacy

The clinical response to evaluate the vaccine efficacy will be assessed by comparing the punch biopsy results between the Screening Visit (having had HSIL to qualify for vaccination) and the 12-Month Visit (\pm 2 weeks) (Fig. 6). LEEP will not be performed to assess efficacy, but it will be offered at no cost to subjects who have persistent HSILs at the 12 Mo Visit.

The design of the proposed Phase II trial is single-site, and randomized to 2 treatment arms in a double-blinded fashion. We will use a historical placebo group from a clinical trial with similar design (i.e., enrollment of subjects with biopsy-proven CIN2/3, and clinical response assessed by biopsy in 15 month) for comparison [57]. The overall histological regression rate in the dose-escalation Phase I clinical trial was 52% three months after the last vaccination, and this is expected to substantially increase with an extended 12-month observation period.[18] Assuming a conservative rate of 60%, n=35 in the PepCan arm would give 91% power (two-tailed, $\alpha=0.05$) for detecting a statistically significant difference from the historical placebo group which had a 29% (34 of 117) regression rate [57]. Although there is greater uncertainty regarding the Candin®-only arm, there is $\geq 90\%$ power to detect a significant differences between the PepCan and Candin® arms under multiple plausible scenarios (for example, regression rates of 67% vs. 29%, or 85% vs. 50%). Forty subjects in each arm will be enrolled to ensure that at least 35 subjects in each would complete the study. While the use of historical placebo group is not as rigorous as having a concurrent placebo group, a concurrent placebo group with biopsy-proven CIN2/3 that would go untreated for 12 months would be difficult to ethically justify.

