4.1 OVERVIEW

This is a single site Phase II clinical trial of PepCan for treating women with biopsy-proven HSILs randomized and double-blinded to two treatment arms. Half of the subjects will receive PepCan, and the other half will receive Candin® alone. The study design closely resembles the latest guidelines for treating young women with HSIL [14]. Study subjects will be patients attending the UAMS Obstetrics and Gynecology Clinics with untreated biopsy-proven HSILs and patients referred from other clinics. Four injections (one every 3 weeks) of PepCan or Candin® will be intradermally administered in the extremities. Clinical response will be assessed by comparison of colposcopy-guided biopsy results obtained prior to vaccination and at 12-Month Visit. Safety will be monitored from the time of enrollment through the 12-Month Visit. Blood will be drawn for laboratory testing and immunological analyses (“blood test”) prior to injection, after the second vaccination, 6 months after the fourth vaccination, and 12 months after the fourth vaccination. Blood will be drawn to aid T-cell analyses (“blood draw”) after the first and third vaccinations, and possibly at the Optional Follow-Up and/or Optional LEEP visits. HPV-DNA testing will be performed at Screening and 6- and 12-Month Visits (Fig. 6). If a subject has persistent HSIL at the 12-Month Visit or if a subject is withdrawn due to excessive toxicity, she will be given an option to return for a LEEP visit. Alternatively, she may choose to exit the study and be followed by a gynecologist for up to 2 years of observation as recommended before surgical treatment [14].

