5.1.1 Inclusion Criteria

- Aged 18-50 years
- Had recent (\leq 60 days) Pap smear result consistent with HSIL or “cannot rule out HSIL” or HSIL on colposcopy guided biopsy
- Untreated for HSIL or “Cannot rule out HSIL”
- Able to provide informed consent
- Willingness and able to comply with the requirements of the protocol

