8 OUTCOME MEASURES

8.1 CLINICAL ASSESSMENTS (UAMS Pathology Laboratory)

Clinical response will be assessed (by Pathologists on service in the Pathology Department) by comparing punch biopsy results from screening (having had HSIL is the inclusion criterion) with the quadrant biopsies performed at the 12-Month visit. The result of the highest grade will be recorded. The subject will be considered a “complete responder” if the 12-Month quadrant biopsies are negative for CIN, a “partial responder” if the show show CIN 1 or a “non-responder” if the biopsy shows HSIL (CIN 2 and/or 3). In addition to the above analysis of subjects who exited after the 12-Month Visit, another analysis may be performed with addition of subjects who exited the study after the 6-Month Visit if histological results (biopsy and/or LEEP) are available at 6 months.

8.2 VIROLOGICAL STUDY (HPV-DNA TESTING ([name] Laboratory) AND BACTERIAL TESTING (University of Chicago Argonne Laboratory))

The ThinPrep samples will be tested for the presence of HPV-DNA. A commercially available kit such as the “Linear Array HPV Genotyping Test” may be used (Roche Molecular Diagnostics, Inc., Alameda, CA). This kit tests for 37 HPV types (6, 11, 16, 18, 26, 31, 33, 35, 39, 40, 42, 45, 51, 52, 53, 54, 55, 56, 58, 59, 61, 62, 64, 66, 67, 68, 69, 70, 71, 72, 73, 81, 82, 83, 84, IS39, and CP6108). The human β -globin signal will also be assayed as a positive control for sample adequacy for DNA content from each sample. Positive-control samples (with added HPV plasmid DNA and plasmid-encoded human β -globin gene) and negative-control samples (no HPV plasmid DNA and no human β -globin gene) will be provided by the manufacturer and will be included in each experiment. HPV types 31, 33, 35, 52, 58, and 67 will be considered “HPV 16-Related”, additionally HPV types 18, 39, 45, 51, 53, 56, 59, 66, 68, 69, 70, 73, and 82 will be considered “High Risk”, and types 6, 11, 40, 42, 54, 61, 62, 71, 72, 81, 83, 84, and CP6108 will be considered “Low Risk” [58]. If samples are still available after HPV testing, other gene sequencing and gene expression studies may be performed for subjects who agreed in the consent for future use of remaining samples.

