This is a Phase II randomized double-blind clinical trial for treatment of cervical intraepithelial neoplasia 2/3 (CIN2/3) with two treatment arms: PepCan and Candida. Because the Phase I results showed Th1 promotion and better clearance of non-HPV 16 infection compared to HPV 16 infection, a Candida-only arm was also included. The design of this clinical trial closely resembles the latest guidelines for treating young women with HSILs. 12 Potential study participants with recent Pap smear results that indicate HSILs or that cannot rule out HSILs are being recruited locally and widely through community-based efforts. The patient's eligibility for vaccination is assessed by explaining the inclusion and exclusion criteria, obtaining medical history (including a list of current medications), and performing a physical examination. The inclusion criteria are (1) women ages 18-50, (2) ability to provide informed consent, (3) willingness to comply with requirements of the protocol, and (4) recent Pap smear report of HSIL or "cannot rule out HSIL" or colposcopy-guided biopsy report of HSIL. The exclusion criteria are (1) history of disease or treatment that has caused immunosuppression, (2) pregnancy or attempting to be pregnant, (3) breast feeding, (4) allergy to Candida antigen, (5) history of severe asthma requiring emergency room visit or hospitalization <5 years, (6) history of invasive squamous cell carcinoma of the cervix, and (7) history of having received PepCan. Colposcopy with biopsy is then performed by a study gynecologist, and a ThinPrep sample for HPV-DNA testing is collected. A blood sample is drawn for a complete blood cell count (CBC; white blood cells [needs to be ≥3K], hemoglobin, hematocrit, platelets [≥50K]) and complete metabolic panel (CMP; ALT, AST, albumin, alkaline phosphatase, total bilirubin, total protein, sodium, potassium, chloride, CO2, BUN, creatinine, calcium, glucose). Subjects with biopsy-confirmed CIN2/3 then proceed to vaccination. The vaccine assignment is randomized to PepCan and Candida (1:1) and is double-blinded. Injections are given intradermally in limbs every 3 weeks, for a total of 4 injections. A urine pregnancy test is performed before each vaccination. CBC, CMP, and immunomonitoring are repeated during visits 1 and 3 and visits at 6 month and 12 month. PepCan is prepared by a research pharmacist by reconstituting lyophilized peptides with sterile water and drawing them in a syringe, along with 300 μL of Candida. Because PepCan and Candida are both colorless, no additional procedures are required for blinding. A nurse administers the vaccine intradermally in a limb. Any immediate AEs are recorded. Subjects are asked to record their symptoms in a diary. At the 6-month visit, colposcopy is performed and biopsies are taken if suspicious for progressing disease. ThinPrep sample for Papanicolaou smear and HPV testing is collected. If the disease is persistent or progressing, subjects would be provided an option to proceed to loop electrical excision procedure (LEEP). At 12-month visit, histological response is assessed by colposcopy-guided 4-quadrant biopsies. Results from each treatment arm will be compared to those from a historical placebo group. 13

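### Protocol 6.4.2 admits an equivocal biopsy to vaccination where the synopsis, 6.4.1 and the SAP require confirmed HSIL or CIN2/3, and no analysis set requires confirmed CIN2/3 at entry

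*Protocol*

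**What the plan says.** **Text that admits an equivocal biopsy.** Protocol 6.4.2 describes the review of screening results that decides whether a woman may be vaccinated. It reads "Eligibility for vaccination includes presence of HSIL or" and continues with the alternative that HSIL cannot be excluded. Both alternatives are tied to the colposcopy-guided biopsy.

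**Text that requires confirmation.**
- Synopsis (1.1), row on eligibility for vaccination: one route only, "recent untreated colposcopy guided biopsy-confirmed HSIL".
- Protocol 6.4.1, immediately before 6.4.2: "HSIL needs to be confirmed to be eligible".
- SAP Overview: "Subjects with biopsy-confirmed CIN2/3 then proceed to vaccination".

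**Text that presupposes HSIL at entry.** Protocol 4.1 describes the trial as "treating women with biopsy-proven HSILs randomized and double-blinded to two treatment arms". Protocol 1.5.9 says of the screening biopsy "having had HSIL to qualify for vaccination", and 8.1 says "having had HSIL is the inclusion criterion".

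**Where the equivocal term otherwise appears as an entry route.** In 5.1.1 it belongs to the smear: "Pap smear result consistent with HSIL or" is followed by the same equivocal category, and biopsy is a separate route that requires HSIL. The synopsis, 5.1 and the SAP Overview use it the same way, for entry to screening.

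**Analysis sets.** Protocol 9.1 bases its main comparison on women who completed the 12-Month Visit and its ITT analysis on all who qualified for vaccination. SAP II.a defines ITT as qualified and randomised, and per-protocol as having completed the 12-month assessment. None of these definitions mentions confirmed baseline histology. Under 8.1 a complete responder is anyone whose 12-month quadrant biopsies show no CIN.

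**The concern.** The primary endpoint is regression of HSIL, and two of the three comparisons in Protocol 2.1 are against a fixed rate from a group that 1.5.9 and 9.1 describe as having biopsy-proven CIN2/3. A woman vaccinated under 6.4.2 who never had HSIL, and who has clean biopsies at 12 months, would count as a complete responder without having regressed from anything. Randomisation does not protect a comparison with an external group, so such women could raise the response rate of either arm above the benchmark with no treatment effect.

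SAP II.d splits the historical per-protocol group by entry diagnosis into CIN2 (18 of 66) and >CIN2 (16 of 51). These add up to 34 of 117, so the whole reference group sits in one of those two strata. A woman with an equivocal entry biopsy has no counterpart in it.

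**Working it through.** **1. The plan's own figure.** Protocol 1.5.9 gives 91% power for PepCan at 60% with n = 35 against 34/117, two-sided α = 0.05. Two-proportion normal formula:
- difference = 0.600 − 0.2906 = 0.3094
- pooled rate = (21 + 34)/152 = 0.3618
- SE under the null = √[0.3618 × 0.6382 × (1/35 + 1/117)] = 0.0926
- SE under the alternative = √[0.24/35 + 0.2906 × 0.7094/117] = 0.0928
- power = Φ[(0.3094 − 1.96 × 0.0926)/0.0928] = Φ(1.378) = 91.6%

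The stated figure reproduces. It is not in dispute.

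**2. Cut-off of the planned test.** The analysis is an exact two-sided binomial test against 29.1%. With n = 35, 15 responders give p = 0.092 and 16 give p = 0.039, so the test first rejects upward at 16. With no effect and all women confirmed, P(X ≥ 16 | 35, 34/117) = 2.7%.

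**3. Adding women without HSIL at entry.** Let m of the 35 be such women, each with chance q of no CIN at 12 months. The other 35 − m respond at 34/117. Responders are then Bin(35 − m, 34/117) + Bin(m, q), and the false-positive chance is the probability that this sum is 16 or more. Neither m nor q is in the documents; both are assumptions.

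| m | q = 30% | q = 50% | q = 75% | q = 100% |
|---|---|---|---|---|
| 0 | 2.7% | 2.7% | 2.7% | 2.7% |
| 2 | 2.7% | 3.8% | 5.3% | 7.0% |
| 4 | 2.8% | 5.2% | 9.7% | 16.2% |

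**4. Shift in the no-effect rate.** This is m(q − 0.2906)/35. For m = 2 and q = 100% it is 2 × 0.7094/35 = 4.1 points. For m = 4 it is 8.1 points at q = 100% and 4 × 0.2094/35 = 2.4 points at q = 50%. When q is near the historical rate the shift is close to zero.

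**5. Cost of restricting the set.** If 2 of 35 women leave, the formula in step 1 gives 90.4% power at n = 33. If 4 leave, it gives 89.1% at n = 31.

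**The case against.** The case for treating this as a small matter is strong, and most of it stands.

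- **Probably a drafting slip.** Wherever else the equivocal term is an entry route it describes the Pap smear, and six other places require or presuppose HSIL at entry. A reader might take 6.4.2 as the operative rule that overrides the rest. The documents do not support that: the synopsis has its own row on eligibility for vaccination, and 6.4.2 is a summary sentence whose limits are set out in 6.4.1. Still, 6.4.2 does describe the eligibility decision, and as written it contradicts 6.4.1.
- **No evidence that it happened.** A reader might infer that women without HSIL were vaccinated. Nothing in the documents shows this. The baseline histology table in SAP I.a would probably reveal any such woman, but would not remove her from an efficacy set.
- **The largest figures are upper bounds.** The 7.0% and 16.2% assume that every such woman has no CIN at 12 months. An equivocal biopsy may be true HSIL, and under the strict criterion in 9.1 residual CIN 1 counts as non-response. With q near 30% there is essentially no inflation.
- **The randomised comparison is largely spared.** By 4.2, randomisation follows confirmation of eligibility, so such women would fall in either arm by chance. The effect on PepCan versus Candin would be mainly dilution.
- **Excluding women changes ITT.** Removing randomised women from the ITT set would redefine it. This is correct, and it limits what the fix should ask for.

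**Conclusion.** The point holds as an internal contradiction in the eligibility text, together with an analysis plan that has no rule to contain its consequences. It bears on the two comparisons with the historical group. In the illustration the upper-tail false-positive chance moves from 2.7% to somewhere in 2.7–7.0% with two such women and 2.8–16.2% with four, for q between 30% and 100%. Those ranges rest on assumed values of m and q, so the actual bias is unknown and may be nil. The documents do not support reading the upper figures as expected values, or concluding that the PepCan-versus-Candin result is compromised.

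**What to change.** 1. Reconcile Protocol 6.4.2 with the synopsis, 6.4.1 and the SAP Overview so that all four state the same qualifying biopsy result. The choice of clinical wording is the sponsor's.
2. In Protocol 9.1 and SAP II.a, keep the ITT set as defined. State that the per-protocol comparison with the historical group is restricted to women with biopsy-confirmed CIN2/3 at entry.
3. Apply the same restriction to the ITT comparison with the historical group as a sensitivity analysis, and report how many women it removes.

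Baseline histology is fixed before randomisation, so the restriction does not select on anything that follows treatment. SAP I.a already tabulates it, so no new data are needed. The cost is one phrase in 6.4.2, a line or two in each of 9.1 and II.a, and possibly a few women fewer in the restricted sets. If no woman was vaccinated on an equivocal biopsy, the results do not change.
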